## 9.0. AIMS

[figure not shown]
The overall goal of our Protocol Leadership Group (PLG) is to produce first-ever evidence on the effectiveness of a proven pragmatic lifestyle intervention targeted at modest, clinically meaningful weight loss and increased physical activity in overweight or obese patients with spirometry-confirmed COPD. In the 12-month simple, pragmatic clinical trial (PCT), we efficiently focus on the intervention effects primarily on exercise tolerance; and secondarily on weight loss, dyspnea, generic and symptom-specific quality of life (QoL), and cardiovascular risk factors (CVRFs).

We will implement the E-LITE self-directed lifestyle intervention in a multicenter, patient-level randomized PCT of approximately 680 overweight and obese patients with COPD. Our specific aims are to test whether, compared with usual care (UC) controls, intervention participants have better outcomes through 12 months of follow-up, including:

1. **Primary measures:** Exercise tolerance measured with the 6-Minute Walk Test (6MWT) distance at 12 months (primary endpoint).
2. **Secondary measures:** Greater weight loss, less dyspnea measured with the modified Borg scale, improvements in generic HRQoL by the SF-12v2, COPD symptom QoL by the SGRQ-C, and major CVRFs (central obesity by waist circumference, Framingham Risk Score, blood pressure, and BMI).

## 10.0. STUDY DESIGN

INSIGHT COPD is a simple, two-arm PCT in which approximately 680 overweight and obese COPD patients, aged 40 years and older, will be randomized to UC or UC plus the self-directed lifestyle intervention for 12 months. Follow-up assessment will occur at 12 months (Figure 4). We hypothesize that intervention participants will have better exercise tolerance at 12 months.

## 10.1. Eligibility Criteria

Eligible patients are age 40 years or older, overweight or obese, have COPD, and have symptoms of dyspnea. Inclusion criteria are broad to protect feasibility and generalizability. Exclusion criteria are aimed at ensuring each participant's safety and maximizing internal validity including minimizing error associated with the primary outcome, and preventing possible missing data. Specific criteria are:

### 10.1.1. Inclusion

- 40 years or older at time of eligibility screening;
- Body mass index 25.0-44.9 kg/m^2;
- Smoked at least 10 pack-years of cigarettes;
- Modified Medical Research Council dyspnea score of 1 or higher, i.e., "I get short of breath when hurrying on the level ...";
- COPD, defined as an FEV1/FVC less than 0.70 and FEV1% predicted greater than 30;
- Access to DVD player or internet in order to view the 12 GLB sessions;
- Consent to the study protocol/procedures including:
  - time and data collection requirements of the study;
  - randomization to one of the two intervention arms;
  - adherence to the recommendations of the study intervention as assigned;
  - authorizing extraction of relevant information from their medical records.

### 10.1.2. Exclusion

- Inability to speak, read, or understand English;
- Active weight loss interventions including:
  - use of prescription weight-loss medications in the past 3 months,
  - current participation in group or individual weight loss programs provided by trained personnel (attending peer support groups or following a self-help weight management book, "boot camp," or diet is not an exclusion),
  - had bariatric surgery or plans to undergo bariatric surgery during the study period;
- Expected weight loss because of alternate explanations, such as from illness;
- Unable to ambulate to weight scale for weight measurement;
- Safety and/or adherence concerns due to severe physical or mental health issues or life expectancy <18 months;
- Pregnant, lactating, or planning to become pregnant during the study period;
- Participation in other intervention studies.

## 10.2. Recruitment, screening, and baseline assessment

NEMO-contracted clinical sites will enroll approximately 680 overweight and obese patients with spirometry-confirmed COPD. Clinical sites will have coordinators identified and trained to perform the protocol. Specific procedures are described in the Manual of Operations.

Patients may be identified in usual approaches including clinic, other patient or provider referrals as in other clinical trials. Given the volume and timeline for the recruitment processes, clinical sites may benefit from using an existing electronic health records (EHR) or clinical/COPD registry.

### 10.2.1. EHR/COPD registry-based pre-screen

Using a Waiver of HIPAA Authorization, the screening process for each cohort begins with identification of individuals who meet the following inclusion criteria using relevant data in the patients' EHR or via a COPD registry as available by the site. Other criteria may be applied according to available resources:

- Age 40 years or older;
- BMI 25.0-44.9 kg/m^2 during the past 6 months;
- Diagnosis of COPD.

### 10.2.2. Initial invitation

Sites send patients identified via the EHR or COPD registry an invitation to participate via EHR-integrated secure messaging (if user), email (if available and allowed by the Institutional Review Board [IRB]), or mail. A letter and/or Information Statement, depending on site IRB requirements, will describe the research activity and instruct patients how to self-screen online, request additional information, or decline further participation by returning an opt out postcard. The invitation also explains that clinical center staff will contact them on behalf of the study to assess interest if they do not respond within 2 weeks.

### 10.2.3. Initial online, telephone, and/or clinic recruitment

Using a *Waiver of Documentation of Informed Consent, or Waiver of Consent* (depending on site IRB requirements), patients identified by any of the above methods, and who desire to be screened may complete a Research Electronic Data Capture (REDCap) on-line self-screen and/or telephone screen with a site coordinator. Those patients who choose to complete the on-line screen will answer brief questions regarding major exclusions (Table 4). If their answers indicate potential eligibility, or if no response has been received after two weeks of sending the invitation, sites contact the potential participant for a more detailed telephone screen. An "Eligibility Pre-review" can be conducted by the sites before contacting the participant (to screen for basic eligibility criteria (if site IRB approved). The telephone screen includes eligibility criteria listed in Table 4. The telephone screening questions may also be asked in-person if recruiting at a pulmonary clinic. If the potential participant is eligible based on their answers to the screening questions, the site coordinator asks spirometry safety questions prior to scheduling an in-person eligibility screen and baseline visit. The safety questions confirm that the participant has no temporary conditions that would preclude the subject from doing spirometry. In the event that the participant has a condition that would preclude testing in the short term, staff should arrange to call the participant back at a later date to complete another telephone screen and schedule the visit then.

Sites may send a paper copy of the baseline questionnaires (SF-12v2 and SGRQ-C) to the potential participant for completion prior to the person's visit. Questionnaires will only be collected after the Informed Consent Form is signed. Table 4 summarizes the screening assessment questions and measures:

**Table 4: On-line, telephone and/or in-person screen**

Assessment/activity	Measure
Send invitation	

• Refusals via postcard

On-line self-screening	Self-report: 

• Age

• Sex

• Pregnancy/lactation for those indicating "female"

• Self-report height and weight for BMI calculation

• Smoking history (yes/no)

• Dyspnea (yes/no)

Telephone/In-person screen: eligibility criteria	Self-report: 
 
• Age
 
• Sex
 
• Pregnancy/lactation for those indicating “female”
 
• Self-report height and weight for BMI calculation [Note: The above completed by phone only if not already done by patient online self-screen]
 
• Smoking pack years
 
• mMRC dyspnea scale score
 
• Weight loss programs/surgery
 
• Participation in other intervention studies
 
• Expected weight loss for other reasons, e.g., illness
 
• Willing/able to complete surveys in English
 
• Willing to participate with intervention protocols
 
• Able to ambulate for weight measurement
 
• Able to return for 12-month follow-up
 
• Access to DVD/internet for GLB sessions
 

Telephone/In-person screen: spirometry safety check [Complete if patient screened eligible]	
 
• Temporary spirometry contraindications             
 
○ Heart attack or unstable angina in last 30 days
 
○ Detached retina or eye surgery within past 30 days
 
○ Breathing problems gotten worse in the last week
 
○ New prescription for antibiotics or oral steroids for acute exacerbation)
 
○ Other
 
 
 

**10.2.4. In-person visit: screen and baseline visit**

All study visits will take place at clinical sites, and require a well-illuminated, quiet, setting that protects patient privacy. In addition, a NEMO certified 6MWT course should be available in the immediate vicinity.

**10.2.4.1. Informed Consent:**

The visit begins with a site coordinator obtaining the participant’s written informed consent. The coordinator reviews with the participant the Informed Consent Form, detailing the responsibility of the participant to INSIGHT COPD, the responsibility of the investigators and staff to the participant, and participant’s personal risks and benefits, the concept of random assignment and what each treatment group involves, and stresses the importance of follow-up assessment even if he/she is not adhering to the assigned treatment. This process meets the ethical obligations to maximize participants’ understanding of information required for an informed decision regarding participation in the INSIGHT COPD trial, and improves retention by developing rapport between the participant and research staff. Each stage in the screening and enrollment process includes a clearly written description of information relevant to that stage and ample opportunities to answer participants’ questions. Even when printed information is provided, research staff must verify that the participant understands what he/she has read and heard.

To maximize retention and assure that participants fully understand the demands and nature of the study before they enroll, recruitment staff will carefully review study requirements with the participants, explain the concept of random assignment and what each treatment involves.

**10.2.4.2. HIPAA Waiver:**

Participants sign a HIPAA authorization in order that sites may review the medical record for eligibility confirmation, to supplement outcome measures as appropriate, and to share the research data with the PLG and NEMO.

### 10.2.4.3. Demographics and confirmation of eligibility:

After the participant has signed the Informed Consent Form, a site coordinator assesses the measures summarized in Table 5 in order to assess the participant’s eligibility. For items already answered via the on-line survey or telephone/in-person screen, answers will be verified to confirm accuracy. Those who are not eligible will be so informed and free to leave.

The table below is a summary of activities included in the consent and eligibility confirmation process. All data will be either directly entered into the INSIGHT COPD REDCap database, or recorded on a paper form for later entry into REDCap. For self-report surveys, the following options are available depending on participant preference and site infrastructure:

- Completion prior to visit: sites may mail surveys to participants for completion at home and will be brought to the study visit. The coordinator will collect the completed surveys *only after* Informed Consent is signed and if the participant is found to be eligible to participate. The coordinator will review the responses for completeness and ask for clarification as necessary. Surveys responses will be entered into REDCap after the visit.
- Completion at the visit: If not completed prior to the visit, participants are strongly encouraged to complete the surveys on paper at the study visit with data entry by the coordinator after the visit. Alternatively, the coordinator may ask participants the questions and enter answers directly into REDCap.

Table 5: Consent, demographics, and eligibility confirmation	
Assessment/activity	Measure
Informed consent and HIPAA authorization	Date of signature acquired (Informed Consent and HIPAA)
Demographics	Self-report: 
 
• Date of birth
 
• Sex
 
• Race
 
• Ethnicity
 
• Marital status
 
• Educational
 
• Employment status
 
• Healthcare and prescription coverage
 

Self-report eligibility criteria (supplement/confirm telephone responses)	Self-report: 
 
• Date of birth
 
• Pregnancy/lactation for those indicating “female”
 
• Smoking pack years
 
• mMRC dyspnea scale score
 
• Weight loss programs/surgery
 
• Participation in other intervention studies
 
• Expected weight loss for other reasons, e.g., illness
 
• Willing/able to complete surveys in English
 
• Willing to participate with intervention protocols
 
• Able to ambulate for weight measurement
 
• Able to return for 12-month follow-up
 
• Access to DVD/internet for GLB sessions
 

Height	Measure height
Weight	Measure weight
BMI	Calculated from height and weight
Spirometry	Measure pre and post bronchodilator: 
 
• FEV1/FVC
 
• FEV1
 

- FVC

#### 10.2.4.4. Additional baseline measures:

For those who are determined to be eligible to participate, the coordinator assesses the measures summarized in Table 6.

Table 6: Additional baseline measures	
Assessment/activity	Measure
Vitals	
 
• Blood oxygen saturation level (SpO2)
 
• Resting heart rate
 

Exercise tolerance	
 
• 6MWT distance
 
• Modified Borg dyspnea and leg fatigue rating pre and post 6MWT
 

CVDR	
 
• Waist circumference
 
• Framingham Risk Score:               
 
○ age
 
○ gender
 
○ smoking status
 
○ systolic BP
 
○ self-report use of BP medication
 
○ self-report diagnosis of diabetes
 
○ self-report use of diabetic or hypoglycemic medication
 
○ BMI
 
 
 
• Blood pressure
 

Self-report surveys	
 
• General health status (SF-12v2)
 
• Health inventory checklist
 
• Medications
 
• Health care utilization
 
• COPD symptoms (SGRQ-C)
 

#### 10.2.4.5. Pre-randomization eligibility and safety screening:

A site study investigator or appropriately qualified designee reviews the participant’s research enrollment record for eligibility, including adequacy of spirometry and existence of any safety concerns and health-related suitability prior to randomization. If deemed appropriate, the coordinator will randomize the participant via REDCap.

### 10.3. **Randomization**

All of the baseline assessment measures listed in Tables 5 and 6 must be completed prior to randomization. A site coordinator will randomize the participant using the REDCap randomization function. The unit of randomization will be the participant, performed at a ratio of 1:1. We will stratify each site on smoking status (current smoker vs. non-smoker). In order to maintain blinding of the outcome assessors to the randomization assignment, sites may choose to:

- Have one coordinator conduct the baseline assessment, conduct randomization, and orient those in the intervention arm to the intervention, then have a different trained coordinator conduct 12-month outcome assessments; or
- After baseline assessment, hand-off the participant to a different coordinator who only will conduct randomization and orient participants to the intervention, and who will not conduct outcome assessments.

#### 10.3.1. **Participants randomized to the intervention**

**Intervention introduction:** A site coordinator provided the intervention materials (Table 7), set the participant up with MyFitnessPal and Fitbit website accounts, and link the account with the INSIGHT COPD lifestyle coach account. A lifestyle coach will introduce the participant to the intervention materials during the phone orientation with procedures including: reviewing the schedule and process for using the 12-weekly GLB DVDs or online videos and handouts and 10 post-core session materials; providing instruction on how to use the Fitbit activity tracker and weight scale for self-tracking; synchronizing the activity tracker with Fitbit.com or mobile application; logging weight, diet, physical activity, and session completion into MyFitnessPal or on Keeping Track Booklets; checking biweekly messages from the lifestyle coach on MyFitnessPal; and contacting the lifestyle coach via MyFitnessPal and phone, and at the participant’s discretion, by email and/or texting.

The INSIGHT COPD trial is using MyFitnessPal instead of Heart360, which was used in E-LITE trial, for the following reasons:

- Ease of use for participants: one login in MyFitnessPal vs. two for Heart360 because the latter requires a HealthVault account as well.
- Availability of dietary self-tracking in MyFitnessPal, but not in Heart360.
- Successful switch from Heart360 to MyFitnessPal in [name] R01s (HL119453 and HS022702), funded after the completion of E-LITE.

**Intervention Orientation:** The lifestyle coach contacts intervention participants via phone within 1 – 2 business days of randomization to schedule a phone orientation session. The orientation session should take place within two weeks of randomization to the extent possible, although deviation from this schedule is permissible to accommodate participants’ scheduling needs and preferences. In the orientation session, the coach will review the program, benefits and options for using his/her lifestyle coaching expertise, and answer any questions (see section 9.6.3. “Intervention Format, Structure, and Content” for additional details).

#### **Table 7: Intervention materials**

- Group Lifestyle Balance™ DVD or online videos
- Post Core Support Physical Activity DVD
- GLB Binder and participant handouts pertinent to the 12-week core intervention activities and to the post-core activities for the remainder of the 12-month intervention
- Weight scale
- Fitbit activity tracker/ instructions/batteries
- The Calorie King™ Calorie, Fat and Carbohydrate Counter book
- Keeping Track Booklets and postage-paid return envelopes (alternative or complement to tracking via MyFitnessPal and Fitbit)
- MyFitnessPal and Fitbit Account Setup Instructions
- Lifestyle coach contact information/options

#### **10.3.2. Participants randomized to the control**

These participants are instructed to continue their usual diet and exercise activities and weight management practices as desired. Control participants will be given a Fitbit activity tracker at their 12-month visit to approximate the weight and activity aids the intervention group received.

#### **10.3.3. All participants**

All participants receive a tote bag, water bottle, and refrigerator magnet that display the INSIGHT COPD logo. The PTC supplies these items to sites.

### **10.4. Time Commitment**

#### **10.4.1. Control group**

- Total time for the coordinator is approximately 3.5 hours.
- Total time for the participants is approximately 2.5 hours.

#### **10.4.2. Intervention group**

- Total time for the coordinator is approximately 4.0 hours.
- Total time for the participants is approximately 3.0 hours.

### 10.5. Follow-up Visit and Data Collection

Participants complete a follow-up visit at 12 months post enrollment. The target time window for completion is +/-2 weeks of the index post-randomization date; however, events outside the influence of the site may prevent this; therefore, it is acceptable to conduct the visit within +/-4 weeks. Visits that occur outside of the acceptable window must be accompanied by justification. Acceptable reasons include participant illness, or inability to reach the participant, participant not able to travel to the site, or suspended visits because of the COVID-19 pandemic. The site is expected to schedule and complete a follow-up site whenever possible even if it falls outside the acceptable window. The staff person conducting these assessments must be different from the person who conducted and oriented the participant to the randomization assignment. The coordinator will assess the measures summarized in Table 8.

Table 8: 12-month measures	
Assessment/activity	Measure
Weight	Measure weight
Vitals	
 
• Blood oxygen saturation level (SpO2)
 
• Resting heart rate
 

Exercise tolerance	
 
• 6MWT distance
 
• Modified Borg dyspnea and leg fatigue rating pre and post 6MWT
 

CVDR	
 
• Waist Circumference
 
• Framingham Risk Score:               
 
○ age
 
○ gender
 
○ smoking status
 
○ systolic BP
 
○ self-report use of BP medication
 
○ self-report diagnosis of diabetes
 
○ self-report use of diabetic or hypoglycemic medication
 
○ BMI
 
 
 
• Blood pressure
 

Self-report surveys	
 
• General health status (SF-12v2)
 
• Health inventory checklist
 
• Medications
 
• Health care utilization
 
• COPD symptoms (SGRQ-C)
 

Spirometry	Measure pre and post bronchodilator: 
 
• FEV1/FVC
 
• FEV1
 
• FVC
 

Intervention adherence	
 
• Self-report DVD viewing: number of sessions viewed self-tracked by participants via MyFitnessPal or paper booklets)
 

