### **10.6.3. Intervention Format, Structure, and Content**

There is a national call for the provision and coverage of multicomponent lifestyle interventions for obesity in primary care settings. The challenge historically with such interventions is that they are often too intensive to implement in the real world. The Centers for Medicare and Medicaid Services (CMS) reimbursement policy promotes brief (15 minutes), lower-intensity (compared with efficacy studies), face-to-face behavioral counseling within a limited timeframe (i.e., 6-12 months). The E-LITE interventions, upon which INSIGHT COPD is modeled, fit this general pragmatic framework with likely better efficiency due to use of technology. The INSIGHT COPD trial will contribute to the evidence base needed to inform and guide policy change, in the context of growing interest and evidence in technology-based interventions.

INSIGHT COPD consists of a 12-month intervention that will have 2 distinct stages: core curriculum (months 1-3) and post core (months 4-12). The core curriculum will be delivered using the GLB DVD or on-line viewing option, with supplementary remote lifestyle coaching at the participant’s discretion. The intervention orientation is described in Section 9.3.1. The coach will contact intervention participants within two weeks of randomization for phone orientation, to review the coach role in the intervention, and describe how participants may request coaching if desired. Also, the coach will send biweekly standardized messages via MyFitnessPal as reminders and/or to reinforce the lifestyle change recommendations in the videos.

The lifestyle coach will monitor intervention adherence by downloading participants' self-monitored data from MyFitnessPal and Fitbit web and mobile technologies. For participants who do not use these tools, they will be instructed to mail their booklets every month. The coach will also document the number and content of contacts with participants in a REDCap database.

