### 10.7. Payments/Remuneration

Recommended study participant remuneration (depending on local IRB requirements) is \$40 for completing the baseline visit and being randomized. For randomized participants, the recommended remuneration is \$110 for completing the 12-month follow-up. Table 9 summarizes recommended participant payments. Control patients will receive a Fitbit and the end of the 12-month visit. Because of the June 2018 protocol change eliminating the 18-month visit, sites should ask participants who have already completed the 12-month visit to return to complete spirometry, receive a Fitbit if they were in the control group, and receive final remuneration.

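### Section 10.5 gives the blinded 12-month assessor an item that exists only in the intervention arm (sessions viewed); this conflicts with the coach-based route in Section 10.6.3 and Table 10 and could disclose the arm before the walk test

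*Combined protocol and SAP*

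**What the plan says.** **Blinding.** Section 10.3 gives two ways of dividing the work between coordinators, with the stated purpose "In order to maintain blinding of the outcome assessors to the randomization assignment". Section 10.5 makes the separation mandatory at 12 months: "The staff person conducting these assessments must be different from the person who conducted and oriented the participant to the randomization assignment". Section 15.0 also describes the coordinators who go through questionnaires with participants as blinded.

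**Who does Table 8.** The sentence straight after the separation rule in Section 10.5 reads "The coordinator will assess the measures summarized in Table 8". Table 8 contains the 6MWT, the Borg ratings, weight, waist circumference, blood pressure, questionnaires and spirometry. Its last row, Intervention adherence, is "Self-report DVD viewing: number of sessions viewed self-tracked by participants via MyFitnessPal or paper booklets".

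**Which arm the row applies to.** Table 7 lists the session videos among the intervention materials. For controls, Section 10.3.2 says "These participants are instructed to continue their usual diet and exercise activities and weight management practices as desired".

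**The other route for the same data.** Section 10.6.3 says "The lifestyle coach will monitor intervention adherence by downloading" the participants' self-monitored data, and that participants who do not use the online tools mail in their booklets monthly. Table 10 places self-monitoring across the whole intervention period, with MyFitnessPal, the booklets and REDCap as sources, and does not mark it as a 12-month measure.

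**The concern.** Participants in a lifestyle trial know their arm, so blinding has to come from the person who runs the 12-month tests. The primary endpoint is a walk test supervised by a coordinator. The post-walk Borg dyspnea rating, a secondary outcome, is taken at the same session. Both can be influenced by how the test is conducted and how the participant is encouraged.

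An assessor who asks how many sessions a participant watched will usually know the arm from the answer, because one arm has sessions and the other has none. If that happens before the walk, the separation of staff in Sections 10.3 and 10.5 no longer protects that participant's primary measurement. The protocol would then have a claim of blinded assessment that its own visit instructions can defeat.

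**Working it through.** No arithmetic settles this point. The documents give no size for assessor bias, and the proposed change leaves the sample size calculation in Section 14.1 untouched. The check is a comparison of the relevant sections.

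1. **Is the 12-month assessor meant to be blinded?** Yes. Section 10.3 states the purpose, Section 10.5 requires a different person, and Section 15.0 calls the coordinators blinded. Section 12.0 protects the blinding of staff who collect follow-up data if the DSMB asks for unblinded results, and the retention table in Section 13.0 repeats the aim.

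2. **Does the assessor's task list include an item that applies to one arm only?** Yes, on the literal text. Section 10.5 assigns Table 8 to the coordinator and exempts no row. The sessions belong to the intervention (Table 7), and controls receive none.

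3. **Does anything give that row to other staff, or place it after the walk?** No section does either. Table 8 lists the row last, but nothing says that table order is visit order.

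4. **Is there a competing instruction?** Yes.

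| Question | Section 10.5 and Table 8 | Sections 10.3.1, 10.6.3, 15.0 and Table 10 |
|---|---|---|
| Who obtains it | The 12-month coordinator | The lifestyle coach, through linked accounts, downloads and mailed booklets |
| When | Listed as a 12-month measure | Through the 12-month intervention period |
| Source | Labelled self-report, but tracked in MyFitnessPal or booklets | MyFitnessPal, booklets, REDCap |
| Who enters it | Not stated for this row | The coach, but Section 15.0 names only diet and physical activity data |

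5. **What has to happen for the primary endpoint to be exposed?** Two things: the coordinator obtains the count at the visit, and does so before the 6MWT and Borg ratings. Section 10.5 permits both and requires neither explicitly.

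6. **Does the coach route close the gap by itself?** Not fully. Session completion is among the items participants log (Sections 10.3.1 and 10.6.3), so the coach can see it. But the REDCap entry sentence in Section 15.0 follows one about diet and physical activity and does not mention session counts. A site coordinator with Table 8 in hand has no instruction to leave the row alone.

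**The case against.** The best case for the plan is that the row names its own source, which is a tracking record and not an interview. The rest of the plan sends those records to the coach: accounts are linked at set-up, the coach downloads the data, and paper users get postage-paid envelopes. No section gives the assessor access to MyFitnessPal or has booklets brought to the visit. Table 8 also contains derived quantities such as the Framingham score, so it can be read as a list of 12-month data elements and not as a script of questions.

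This is a fair reading, and it defeats any claim that the plan necessarily unblinds the assessor. It does not remove the conflict. Section 10.5 still assigns the row to the coordinator, still labels it self-report, and says nothing that would stop a coordinator from asking.

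A reader might draw three stronger conclusions that the documents do not support:

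- **That the control-arm Fitbit also unblinds the walk.** Section 10.7 says "Control patients will receive a Fitbit and the end of the 12-month visit", an evident slip that places the handover at the end of the visit. What is missing is only who hands it over and whether outcomes are entered first.
- **That assessor blinding is the sole safeguard for the 6MWT.** The plan also requires testing to ATS guidelines (Section 11.2), a NEMO-certified course (Section 10.2.4), and site training and staff certification (Section 17.0).
- **That a particular inflation of type I error follows.** Any such figure would need an assumed shift in metres, and the documents give no basis for one. In an open behavioural trial participants may also disclose their arm unprompted, so the added effect of this one row cannot be isolated.

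**Conclusion.** The concern holds as an unreconciled conflict between Section 10.5 with Table 8 on one side and Sections 10.3, 10.6.3 and 15.0 with Table 10 on the other. Followed literally, the 12-month instructions can reveal the arm to an assessor whom the plan intends to keep blinded. They can do so before the primary endpoint only if the count is obtained at the visit and ahead of the walk.

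The size of any resulting bias is unknown, and no estimate is offered. The conclusion rests on two readings: that assigning Table 8 to the coordinator covers every row, since none is exempted, and that table order does not fix visit order. It does not show that blinding was in fact broken at any site. The point is worth correcting because the safeguard matters for the primary endpoint and the repair costs almost nothing.

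**What to change.** 1. In Section 10.5, remove the Intervention adherence row from the measures that the blinded coordinator assesses.
2. State in Sections 10.5 and 10.6.3 that session counts come from the coach's MyFitnessPal and booklet records.
3. Extend the data-entry sentence in Section 15.0 so that the coach also enters session counts in REDCap.
4. If a count must still be obtained at the visit, have unblinded staff collect it after all outcome measures are done and entered.
5. As a minor addition to Sections 10.3.2 and 10.7, state that unblinded staff hand over the control-arm Fitbit after outcomes are entered.
6. For 12-month visits already completed, document who obtained session counts and when, so that any description of the assessment as blinded can be supported.

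The cost is protocol wording and a short note to sites. Section 10.5 already requires a second staff member, and the coach already receives the tracking records. Sample size, power and the analysis model are unaffected.
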